3.2.3 Clinical time-to-event outcomes

A secondary important objective of this trial is to assess whether the intervention will be associated with decreased clinical outcomes with 12-months. The endpoint of interest would be the composite of all-cause death; hospitalization for: MI, stroke, decompensated heart failure, or urgent revascularization (coronary, peripheral, carotid). This endpoint will be measured in days from enrollment date to event date for those patients with an event; otherwise to time of last contact date for those patients without an event, ie censored. Each of the clinical time-to-first event outcomes will also be summarized individually with no formal statistical testing, ie will be

presented as hazard ratios (HRs) and 95% CIs. Estimates of the event rates by study arms will be displayed graphically using Kaplan-Meier cumulative risk⁴. Cox proportional hazards model with shared frailty⁵ (ref) to account for clustering effect will be used to estimate unadjusted HR (95% CI). The primary analysis will be a multivariable Cox proportional hazards model with shared frailty to account for clustering effect, adjustment for pre-specified baseline factors (see Appendix 1, Section 8.1 for list).

4. Tertiary Endpoints

All-cause mortality, as assessed by vital status obtained through the National Death Index or other sources will be assessed at 2 and 5 years after the final visit. Patient death will be reported to Boehringer Ingelheim (BI) as an adverse event if the patient was known to be on BI medication for the treatment of T2DM.

5. Implementation Endpoints

At 12 months from site randomization, a provider survey to be completed by the site investigator will be conducted to collect the following information:

- Acceptability of educational intervention
- Appropriateness of educational intervention

Provider survey data will be summarized as the mean (SD), median (25th, 75th percentiles) for continuous variables, and as counts (percentages) for categorical variables by intervention arm. Depending on the primary results and site variation in implementation, we may explore the association between site implementation and the primary outcome.

6. Electronic Health Record Sub-study

A subset of sites with existing datamarts containing EHR data will be included in an observational analysis to describe the clinical characteristics, management, and outcomes of patients with T2DM and CVD in current practice across an array of health systems and to characterize trends in the quality of care for patients with T2DM and CVD over time. These data will not be used to assess the effect of the intervention. A detailed description of the EHR sub-study endpoints and analysis will be contained in a separate statistical analysis plan.

7. Subgroup Analysis

The primary outcome will be assessed for the subgroups using the same methods as the primary analysis. Results of the subgroup analysis will be presented graphically with a forest plot. We will assess the following subgroups:

Subgroups:

- Age: Age ≥ 65 and age < 65
- Sex: Males and females
- Race: White, Black, and Asian/Other
- LVEF ≥ 40 and LVEF < 40
- History of heart failure and no history of heart failure
- History of atrial fibrillation and no history of atrial fibrillation

8. References

1. Team RC. R: A language and environment for statistical computing. 2013
5. Austin PC. A Tutorial on Multilevel Survival Analysis: Methods, Models and Applications. *Int Stat Rev*. 2017 August ; 85(2): 185–203.

9. Appendix 1: Covariates of Interest

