We will follow the guidance and standards for reporting of key elements based on the CONSORT statement for cluster randomized studies². Key elements will include the following items: descriptions of participants, interventions, objectives, outcomes, and sample size justification; and details about the randomization procedure, factors used to stratify randomization, (lack of) blinding, statistical methods, participant flow, dates of recruitment, baseline data by individuals and by cluster, numbers analyzed, outcomes and estimation, adverse events, and a discussion.

Trial population details, including the number of sites randomized, number of patients, median and range of number of patients across sites, the number of patients in intensive and basic arms,

and the number of patients lost to follow-up, withdrawn, or excluded from analyses will be presented in a flow diagram (Appendix 3. Figure 1).

All analyses will be conducted using SAS version 9.4 or higher software. All tests will be two-sided and a p-value of <0.05 will be considered statistically significant. As this is a cluster randomized trial, all p-values will account for site.

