# of patients enrolled		
Location: Urban Non-urban		
Average baseline composite score (enrolled patients)		

Table 3. Effects of the Intervention on Guideline Recommended Medications

Analysis	No./Total (%) at last follow-up		Unadjusted		Adjusted	
	Intervention	Usual Care	OR (95% CI)	P-value	OR (95% CI)	P-value
Primary Outcome: Composite Score of 3						
Prescribed by Cardiologist: Achieving guideline-recommended therapy for T2DM ACEi/ARB treatment High-intensity statin treatment Achieving a composite score of ≥ 2						
Prescribed by Any Provider: Achieving guideline-recommended therapy for T2DM ACEi/ARB treatment High-intensity statin treatment Achieving a composite score of ≥ 2						

Table 4. Effects of the Intervention on Continuous Intermediate Endpoints at last follow-up

Analysis	Intervention			Usual Care			Unadjusted		Adjusted	
	Baseline N, Mean (SE)	Follow-up Mean (SE)	Difference	Baseline N, Mean (SE)	Follow-up Mean (SE)	Difference	Coefficient (SE)	P-value	Coefficient (SE)	P-value
sBP										
dBp										
HbA1c										
LDL-C										

SE- Standard Error

Population includes patients with data at both time points

Table 5. Effects of the Intervention on Achieving Targets at last follow-up

Analysis	Intervention		Usual Care		Unadjusted		Adjusted	
	Baseline No./Total (%)	Follow-up No./Total (%)	Baseline No./Total (%)	Follow-up No./Total (%)	OR (95% CI)	P- value	OR (95% CI)	P-value
sBP<130 mmHg dBP<80 mmHg HbA1c<8% LDL-C<70 mg/dL Composite score of achieving all targets								

Population includes patients with data at both time points

Table 6. Effects of the Intervention on Clinical time-to-first event endpoints within 12 months

Analysis	Cumulative Incidence (95% CI)		Unadjusted		Adjusted	
	Intervention	Usual Care	HR (95% CI)	P- value	HR (95% CI)	P- value
Composite of all-cause death; hospitalization for: MI, stroke, decompensated heart failure, or urgent revascularization (coronary, peripheral, carotid)						
All-cause death						
Hospitalization for MI						
Hospitalization for Stroke						
Hospitalization for decompensated heart failure						
Hospitalization for urgent revascularization						

11. Appendix 3: Figure Shells

Figure 1: Trial Population Flow Diagram

[figure not shown]

Figure 2: Changes in Composite Score and Components over time by Intervention

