Figure 3: Kaplan-Meier Cumulative Incidence of composite of all-cause death; hospitalization for: MI, stroke, decompensated heart failure, or urgent revascularization by Intervention

Figure 4: Kaplan-Meier Cumulative Incidence of all-cause death by Intervention

Figure 5: Kaplan-Meier Cumulative Incidence of hospitalization for MI by Intervention

Figure 6: Kaplan-Meier Cumulative Incidence of hospitalization for stroke by Intervention

Figure 7: Kaplan-Meier Cumulative Incidence of hospitalization for decompensated heart failure by Intervention

Figure 8: Kaplan-Meier Cumulative Incidence of hospitalization for urgent revascularization by Intervention

Figure 9: Forest plot of Odds Ratios for Composite Score Comparing Intervention vs. Usual Care by subgroup

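### Kaplan-Meier slightly overstates cumulative incidence for the four hospitalization-only endpoints, and the SAP names no variance method, clustered or otherwise, for the per-arm intervals in Table 6

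*SAP*

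**What the plan says.** SAP section 3.2.3 defines the composite of all-cause death and the four kinds of hospitalization, and states that "Estimates of the event rates by study arms will be displayed graphically using Kaplan-Meier cumulative risk". Its censoring rule, written for the composite, runs to the event date, "otherwise to time of last contact date for those patients without an event, ie censored". There is no separate rule for a patient who dies without the hospitalization being analysed. The components are to be summarized individually as hazard ratios with 95% CIs and without formal testing.

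The figure shells in SAP Appendix 3 use the Kaplan-Meier label for every clinical outcome. Figures 3 and 4 cover the composite and all-cause death. Figures 5 to 8 cover the single hospitalization endpoints, for example "Figure 5: Kaplan-Meier Cumulative Incidence of hospitalization for MI by Intervention" and "Figure 7: Kaplan-Meier Cumulative Incidence of hospitalization for decompensated heart failure by Intervention".

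The results table in SAP Appendix 2 is "Table 6. Effects of the Intervention on Clinical time-to-first event endpoints within 12 months". Its per-arm columns are headed "Cumulative Incidence (95% CI"), with neither an estimator nor a variance method named.

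On clustering, SAP section 2 says "As this is a cluster randomized trial, all p-values will account for site". Section 3.2.3 adds a shared frailty to the Cox models, both unadjusted and adjusted. Neither document mentions competing risks, a cumulative incidence function, or a clustered variance for the per-arm incidences.

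**The concern.** There are two separate issues.

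The first is the estimator. A patient who dies can no longer be hospitalized for MI. Kaplan-Meier with that death censored treats the patient as still at risk beyond the censoring time, and so estimates the risk in a setting where nobody dies first. Cumulative incidence, the quantity named in the table and figures, is the proportion who actually have the event in the presence of death. For the four hospitalization endpoints the label and the estimator therefore refer to different quantities, and the estimate is the larger one whenever deaths occur.

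The second is precision. The usual Kaplan-Meier variance treats patients as independent, whereas here they are grouped in clinics. The plan's commitments on clustering cover p-values and hazard ratios but not the per-arm intervals. A programmer working from this text could well produce unadjusted intervals and print them beside hazard ratios that do allow for site.

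At stake is the accuracy of the absolute event rates and their stated precision in the planned results table for what section 3.2.3 treats as an important secondary objective. No test or treatment comparison depends on them.

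**Working it through.** **The plan's own figure.** The documents give no event rate, mortality or ICC for the clinical outcomes. The only stated figure that uses the clustering inputs is the power for the primary outcome (SAP section 1.3): 21 sites per arm, 25 patients per site, 10% versus 20%, ICC 0.05, two-sided alpha 0.05.
- Design effect: 1 + (25 − 1) × 0.05 = 2.2.
- Effective sample size per arm: 525 / 2.2 = 238.6.
- Power: 86.7% with a pooled normal test, 85.4% with a t reference on 40 degrees of freedom.

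This agrees with the stated minimum of 85%. The present point does not touch it.

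**Competing death.** Assumptions: constant hazards over 12 months, a Kaplan-Meier hospitalization risk of 5%, and 12-month mortality D.
- Hospitalization hazard: h_e = −ln(0.95) = 0.0513. Death hazard: h_d = −ln(1 − D).
- One minus Kaplan-Meier with deaths censored: 1 − exp(−h_e) = 5.00%.
- Aalen-Johansen: h_e / (h_e + h_d) × [1 − exp(−(h_e + h_d))].

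| D | h_d | Aalen-Johansen | Excess (points) | Relative excess |
|---|---|---|---|---|
| 2% | 0.0202 | 4.950% | 0.05 | 1.0% |
| 3% | 0.0305 | 4.925% | 0.07 | 1.5% |
| 5% | 0.0513 | 4.875% | 0.13 | 2.6% |
| 6% | 0.0619 | 4.850% | 0.15 | 3.1% |

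The relative excess is almost the same for hospitalization risks of 1 to 5%. For scale, the half-width of an unadjusted 95% CI at 5% with 525 patients per arm is 1.96 × √(0.05 × 0.95 / 525) = 1.9 points. If mortality were 2% in one arm and 3% in the other, the two biases would differ by only 0.02 to 0.03 points.

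For the composite and for all-cause death, death is itself an event and does not compete, so Kaplan-Meier is appropriate.

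**Clustering, if the default variance is used.** Let m be the number of patients per site: 25 from the sample size sections, 30 from the enrolment target in the SAP introduction. The event ICC is an assumption. Design effect = 1 + (m − 1) × ICC; shortfall in width = 1 − 1/√(design effect); coverage of a nominal 95% interval = 2Φ(1.96/√(design effect)) − 1.

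| m | ICC | Design effect | Too narrow by | Coverage |
|---|---|---|---|---|
| 25 | 0.005 | 1.12 | 6% | 93.6% |
| 25 | 0.01 | 1.24 | 10% | 92.2% |
| 25 | 0.02 | 1.48 | 18% | 89.3% |
| 30 | 0.005 | 1.145 | 7% | 93.3% |
| 30 | 0.01 | 1.29 | 12% | 91.6% |
| 30 | 0.02 | 1.58 | 20% | 88.1% |

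In the 5% example, the 1.9-point half-width becomes 2.1 points at ICC 0.01 (1.86 × √1.24) and 2.3 points at ICC 0.02 (1.86 × √1.48), both with m = 25.

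**The case against.** The strongest reply is that this concerns a descriptive display. The treatment comparison rests on hazard ratios with a shared frailty for site, all p-values account for site, the components have no formal testing, and the protocol says clinical outcomes are not the primary objective. All of that stands and limits the weight of the point.

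It is also fair to say that the SAP never states how the Table 6 intervals are computed. A reader might infer that they are unadjusted and therefore too narrow. The documents do not say so: the method is unspecified, and the narrowing follows only if the default Kaplan-Meier variance is used. Nor do they mention error bars on the curves.

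A reader might also apply the ICC of 0.05 from the sample size section, which would make the intervals 33 to 36% too narrow. That value was chosen for the prescribing composite. Nothing in the documents supports it for clinical events.

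Finally, a reader might expect the Kaplan-Meier rates to conflict with the hazard ratios beside them. They would not. Clustering leaves the Kaplan-Meier point estimate unchanged, and one minus Kaplan-Meier with deaths censored is a direct function of the cause-specific hazard that the Cox model compares. It is the Aalen-Johansen estimate that also depends on the death hazard and need not track that ratio, so the hazard ratios need a clear label if the estimator is changed.

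What the reply does not remove is the mislabelling in Figures 5 to 8, where Kaplan-Meier is named explicitly, and the gap in the specification of Table 6.

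**Conclusion.** The point holds in a limited form. For the four hospitalization-only endpoints, the plan names Kaplan-Meier for a quantity it calls cumulative incidence, has no competing-risk method, and so overstates that quantity if deaths are censored. The excess is small, about 1 to 3% relative under assumed mortality of 2 to 6% and constant hazards, and lies well inside the sampling error. It would be wrong to conclude that all the reported incidences are too high: the composite and all-cause death are correctly handled.

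For the per-arm intervals, the finding is that no variance method is stated and that the commitments on site adjustment do not reach them. The possible narrowing of 6 to 20% is conditional on the default variance, an assumed event ICC of 0.005 to 0.02, and equal clusters of 25 to 30. It is potentially the larger of the two effects. The hazard ratios, their intervals and the primary analysis are unaffected.

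**What to change.** - In SAP section 3.2.3, Table 6 and Figures 5 to 8, specify the Aalen-Johansen cumulative incidence with death as a competing event for the four hospitalization endpoints, and retitle the figures accordingly. Keep Kaplan-Meier for the composite and for all-cause death.
- State how the Table 6 per-arm CIs are computed: a site-clustered robust variance, or a bootstrap that resamples sites, where event counts allow. At a 1% risk there would be only about 5 events per arm (525 × 0.01) across 21 sites, and a site bootstrap would be unstable. In such cases, label the interval as not adjusted for clustering.
- Keep the shared-frailty Cox hazard ratios and describe them as cause-specific for the hospitalization endpoints.

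The cost is SAP wording, minor programming and somewhat wider per-arm intervals. No new data are needed: vital status is already collected at the follow-up contacts (protocol Table 3), and the composite already requires dates of death. Design and sample size do not change.

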9.1 Potential Adjustment Variables for Primary Outcome Model

Variable	Variable Type
Intervention	yes/no
Site: Urban vs. non-urban	yes/no
Age	continuous
Male sex	yes/no
Race	categorical (Black, Asian/Other, vs. White)
Baseline composite score	ordinal (0-2)

Charlson Comorbidity Index (CCI)	categorical (severe defined as CCI scores ≥ 5 , moderate defined as CCI scores of 3–4, vs. mild defined as CCI scores of 1–2)
Baseline systolic BP	continuous
Baseline diastolic BP	continuous

9.2 Potential Adjustment Variables for Binary Intermediate Outcome Models

Variable	Variable Type
Intervention	yes/no
Site: Urban vs. non-urban	yes/no
Age	continuous
Male sex	yes/no
Race	categorical (Black, Asian/Other, vs. White)
Baseline composite score	ordinal (0-2)
Charlson Comorbidity Index (CCI)	categorical (severe defined as CCI scores ≥ 5 , moderate defined as CCI scores of 3–4, vs. mild defined as CCI scores of 1–2)
**Achievement of Baseline HbA1c < 8%	yes/no
Achievement of Baseline systolic BP < 130 mmHg	yes/no
Achievement of Baseline diastolic BP < 80 mmHG	yes/no
**Achievement of Baseline LDL-C < 70 mg/dL	yes/no
Interaction* between intervention and achievement of baseline target	combination of intervention (yes/no) and achievement of baseline target (yes/no)

*For each outcome, we will test for interaction between intervention and achievement of that baseline target.

**Only the HbA1c and LDL-C outcomes will be adjusted for achievement of these Baseline metrics due to the rate of not drawn for these labs.

10. Appendix 2: Table Shells

Table 1. Patient-level Baseline characteristics by Intervention

PATIENT CHARACTERISTICS	Intervention	Usual Care
Age		
Sex		
Race: White Black Asian Other		
Ethnicity: Hispanic/Latino Not reported		
Insurance/payer: Medicare Part D Supplemental Plan Medicaid Private State-specific (non-Medicaid) Military health care Indian health services Other US insurance		
Medication prescription:		
Lipid lowering therapy: Statin: Low intensity Moderate intensity High intensity Ezetimibe Fibrate Niacin PCSK-9 Prescription-grade Omega 3 FA		
Glucose-lowering therapy: Metformin Insulin Sulphonylurea DPP4 Thiozolidinedione GLP-1RA SGLT-2		

Other Severity: Monotherapy > 1 glucose-lowering medication Average insulin dose		
Anti-hypertensive therapy ACE/ARB Beta-blocker Diuretic Calcium channel blocker MRA		
Anti-thrombotic therapy Aspirin P2Y12 receptor antagonist Warfarin DOAC		
Cardiovascular history		
Coronary artery disease Prior MI Prior CABG Prior PCI Obstructive ($\geq 50\%$) CAD (CT/ICA)		
Cerebrovascular disease: Prior ischemic stroke Carotid artery stenosis ($> 50\%$)		
Peripheral arterial disease: Prior peripheral revascularization Prior amputation due to poor circulation History of Claudication with ABI < 0.9		
Atrial fibrillation		
Heart failure		
Hypertension		
Dyslipidemia		
Cigarette smoking		
Non-Cardiovascular		
Charlson Index		
Diabetes history		
Time since diabetes diagnosis < 1 year		

> 1 to 5 years >5 to 10 years >10 years		
History of DKA		
Complications Retinopathy Neuropathy Diabetic foot Gastroparesis		
Physical characteristics		
Blood pressure SBP DBP		
Heart rate		
BMI		
Laboratory characteristics		
Lipids LDL HDL TG		
eGFR		
HbA1c		
Urine albumin-to-creatinine ratio <30 mg/g 30-300 mg/g >300 mg/g		

Table 2. Site-level baseline characteristics by Intervention

CLUSTER CHARACTERISTICS	Intervention	Usual Care
# of patients enrolled		
Location: Urban Non-urban		
Average baseline composite score (enrolled patients)		

Table 3. Effects of the Intervention on Guideline Recommended Medications

Analysis	No./Total (%) at last follow-up		Unadjusted		Adjusted	
	Intervention	Usual Care	OR (95% CI)	P-value	OR (95% CI)	P-value
Primary Outcome: Composite Score of 3						
Prescribed by Cardiologist: Achieving guideline-recommended therapy for T2DM ACEi/ARB treatment High-intensity statin treatment Achieving a composite score of ≥ 2						
Prescribed by Any Provider: Achieving guideline-recommended therapy for T2DM ACEi/ARB treatment High-intensity statin treatment Achieving a composite score of ≥ 2						

Table 4. Effects of the Intervention on Continuous Intermediate Endpoints at last follow-up

Analysis	Intervention			Usual Care			Unadjusted		Adjusted	
	Baseline N, Mean (SE)	Follow-up Mean (SE)	Difference	Baseline N, Mean (SE)	Follow-up Mean (SE)	Difference	Coefficient (SE)	P-value	Coefficient (SE)	P-value
sBP										
dBp										
HbA1c										
LDL-C										

SE- Standard Error

Population includes patients with data at both time points

Table 5. Effects of the Intervention on Achieving Targets at last follow-up

Analysis	Intervention		Usual Care		Unadjusted		Adjusted	
	Baseline No./Total (%)	Follow-up No./Total (%)	Baseline No./Total (%)	Follow-up No./Total (%)	OR (95% CI)	P- value	OR (95% CI)	P-value
sBP<130 mmHg dBP<80 mmHg HbA1c<8% LDL-C<70 mg/dL Composite score of achieving all targets								

Population includes patients with data at both time points

Table 6. Effects of the Intervention on Clinical time-to-first event endpoints within 12 months

Analysis	Cumulative Incidence (95% CI)		Unadjusted		Adjusted	
	Intervention	Usual Care	HR (95% CI)	P- value	HR (95% CI)	P- value
Composite of all-cause death; hospitalization for: MI, stroke, decompensated heart failure, or urgent revascularization (coronary, peripheral, carotid)						
All-cause death						
Hospitalization for MI						
Hospitalization for Stroke						
Hospitalization for decompensated heart failure						
Hospitalization for urgent revascularization						

11. Appendix 3: Figure Shells

Figure 1: Trial Population Flow Diagram

[figure not shown]

Figure 2: Changes in Composite Score and Components over time by Intervention

Figure 3: Kaplan-Meier Cumulative Incidence of composite of all-cause death; hospitalization for: MI, stroke, decompensated heart failure, or urgent revascularization by Intervention

Figure 4: Kaplan-Meier Cumulative Incidence of all-cause death by Intervention

Figure 5: Kaplan-Meier Cumulative Incidence of hospitalization for MI by Intervention

Figure 6: Kaplan-Meier Cumulative Incidence of hospitalization for stroke by Intervention

Figure 7: Kaplan-Meier Cumulative Incidence of hospitalization for decompensated heart failure by Intervention

Figure 8: Kaplan-Meier Cumulative Incidence of hospitalization for urgent revascularization by Intervention

Figure 9: Forest plot of Odds Ratios for Composite Score Comparing Intervention vs. Usual Care by subgroup
